2 PROTOCOL SYNOPSIS

C 4 1	TO 4 1
TILL 17	1111
Study	11116
~ • • • • • • • • • • • • • • • • • • •	

Effects of A3309, an Ileal Bile Acid Transport Inhibitor, on Gastrointestinal and Colonic Motor Functions in Patients with Functional Constipation

Study code

A3309-003

Principal Investigator

[name] M.D.

Professor of Medicine and Physiology,

Division of Gastroenterology and Hepatology,

Medical Director, Strategic Alliances, Mayo Clinic

Study period	Phase of development
Estimated date of first patient enrolled: January 2010	П
Estimated date of last patient completed: November 2010	

Study design

This is a single-center, randomized, parallel group, double-blind, placebo-controlled, dose response, pharmacodynamic and pharmacokinetic study evaluating the effects of A3309 on gastric, intestinal and colonic transit in patients with functional constipation. Doses of 15 or 20 mg A3309 or matching placebo will be administered orally once daily for fourteen (14) consecutive days.

Aim

To assess the dose related effects of A3309 on small bowel and overall colonic transit and bowel function in patients with functional constipation.

Primary endpoint:

Colonic geometric center at 24 h as measured by scintigraphy, as compared to placebo.

Secondary endpoints:

- 1. Colonic filling at 6 h measured by scintigraphy, as compared to placebo.
- 2. T_{1/2} of ascending colon emptying measured by scintigraphy, as compared to placebo.
- 3. Colonic geometric center at 48 h measured by scintigraphy, as compared to placebo.
- 4. $T_{1/2}$ of gastric emptying of solid
- 5. Assess the effects on stool frequency and consistency based on the Bowel Pattern Diary and effects on symptom parameters coupled to constipation as well as the overall treatment effect, as compared to placebo based on a six question survey given at the end of the pre-treatment period and the post-treatment period.
- 6. Evaluate the pharmacokinetic (PK) and pharmacodynamic characteristics for each dose of A3309.
- 7. Assess the safety and tolerability of A3309 administered as an oral tablet.

Number of patients planned

Twelve female patients with functional constipation in each treatment group for a total of 36 patients.

Diagnosis and main eligibility criteria

Patients with diagnosed functional constipation will be recruited from the local community by public advertisement placed within areas of Mayo Clinic or by a targeted mailing of an informational letter.

Methodology

Female patients with functional constipation will be screened for eligibility and informed about the study during pre-screening dialogue and also at the initial Visit 1 screen.

Within seven (7) to fourteen (14) days of Visit 1, eligible patients will return for an abbreviated scintigraphy test with images obtained only at 4 and 24 hours post In¹¹¹ capsule ingestion. A geometric center at 24 hours must be less than 2.30, the median of normal colonic transit in normal healthy volunteers (as determined by analysis of a compilation of prior [name] studies), to qualify for randomization to study medication, either 15 or 20 mg A3309 or placebo administered orally once daily for fourteen (14) consecutive days. The allocation to treatment group will be concealed.

A urine pregnancy test will be performed for all females of child bearing potential at Visit 1 and again within the 48 hours prior to the receipt of radiation for both the abbreviated and post-study medication transit scintigraphy tests at Visit 2 and Visit 4. Note that females who are status post bilateral tubal ligation, hysterectomy or postmenopausal are exempted from this test.

Study medication will be administered at the Charlton 7 Clinical Research Unit (CRU) at Visit 4, 5, and 6, the days of scintigraphic assessment of gastric, small bowel and colonic transit of solids performed over a 48 hour period.

Within seven (7) to ten (10) days of Visit 6, patients will return to the Charlton 7 CRU for final safety monitoring and an exit physical examination and interview with study staff.

Investigational product, dosage and mode of administration

Patients will take 15 or 20 mg of A3309 or placebo administered orally for eleven (11) consecutive days and report for post-study medication transit scintigraphy on day twelve (12) of dosing. Study medication will be administered once with the In¹¹¹ capsule on Visit 4 and once immediately before the camera images obtained on Visits 5 and 6. Study medication will be administered at Charlton 7 CRU by CRU nurses.

Duration of treatment

A3309 or matching placebo will be administered orally once daily for fourteen (14) consecutive days.

Duration of patients involvement in the study

Each patient will attend seven (7) visits at the clinic during a period of about thirty-one (31) to forty-one (41) days.

Efficacy assessments

- Scintigraphic small bowel and colonic transit
- Assessment of stool frequency and consistency using the Bowel Pattern Diary
- Symptoms of constipation
- Overall treatment effects

Pharmacokinetic and pharmacodynamic analysis

Blood samples for analysis of pharmacokinetic (PK) parameters will be collected at Visit 4, before dosing and at 30, 60, 90, 120, 180, 240, 360, 480 minutes post dosing. Pharmacodynamic parameters (C4, total cholesterol, HDL, LDL and triglycerides) will be collected at Visit 1, Visit 4 and Visit 7.

PK parameters will be analyzed using conventional analyses by Covance, UK

Safety assessments

The following safety assessments will be performed:

- Laboratory safety tests, including a complete blood count (CBC), a comprehensive metabolic panel (CMP), coagulation studies and a urinalysis (UA) performed at Visit 1 study entry, Visit 4 transit scintigraphy and Visit 7 study completion. A urine screen for drugs of abuse will be performed once at Visit 1 study entry.
- A 12-lead ECG performed at Visit 1 study entry, Visit 4 and Visit 7 study completion.
- A physical examination by a study physician at Visit 1 study entry, Visit 6 and Visit 7 study completion and as necessary throughout the study.
- Weight and vital signs (including temperature, pulse, blood pressure and respiration rate) at every visit
- Urine pregnancy tests performed at Visit 1 study entry and within 48 hours prior to receipt of radiation during the abbreviated transit scintigraphy and post-study medication transit scintigraphy at Visit 2 and Visit 4, respectively
- Interview for concomitant medications and adverse events at every visit

Statistical methods

An analysis of covariance (ANCOVA) will be used to compare transit parameters and patient bowel pattern diary summaries (ie, stool frequency, mean stool consistency and mean ease of passage scores) among the treatment groups. The covariates considered for inclusion in the analyses are age, body mass index (BMI) and the corresponding baseline (pre-treatment) bowel pattern diary summaries. If necessary a suitable transformation for potential skewness in the distributions of measured responses or heterogenous variation among treatment groups may be used (e.g., ANCOVA on ranks or square root, transformed stool frequency.)

If the ANCOVA test for overall treatment effects for a given response has a p value less than or equal to 0.10, then both the 15 mg and 20 mg doses will be compared to placebo using Dunnett's test.

Since each of the primary endpoints assesses a separate hypothesis regarding the effects of A3309, no adjustment in the alpha level for testing multiple types of endpoints is anticipated, and a two-sided significance level of 0.05 will be used in each ANCOVA model.

Statistical Power

Based on data acquired using the same methods in the laboratory, the sample size of 12 patients per group provides 80% power to detect differences of approximately 27% to 37% in colonic transit, the primary endpoints. This magnitude of change is considered clinically significant.

Pharmacokinetic and Pharmacodynamic analyses

Plasma concentration of A3309 vs time curves will be plotted for each subject, on both linear/linear and log₁₀/linear scales. Mean plasma concentration vs time curves will also be presented by dose, PK and PD parameters.. Exploratory analyses of the PD variables will be conducted and described in the Statistical Analysis Plan (SAP).

Efficacy analyses

Exploratory analyses of the efficacy variables will be conducted and described in the Statistical Analysis Plan (SAP).

Analysis data sets

The primary analyses will follow the intent to treat (ITT) paradigm with all patients randomized included in the analyses. Those patients with missing response values will have their missing values imputed via the overall (patients with non-missing data) mean and a corresponding adjustment in the ANCOVA residual error variance degrees of freedom (subtracting one for each missing value imputed).

Safety data will be presented for all patients receiving investigational product.

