9 STUDY AIMS AND ENDPOINTS

9.1 Aim

To assess the dose related effects of A3309 on small bowel and overall colonic transit and bowel function in patients with functional constipation.

9.2 Primary endpoint:

Colonic geometric center at 24 h as measured by scintigraphy, as compared to placebo.

9.3 Secondary endpoints:

- 1. Colonic filling at 6 h measured by scintigraphy, as compared to placebo.
- 2. $T_{1/2}$ of ascending colon emptying measured by scintigraphy, as compared to placebo.
- 3. Colonic geometric center at 48 h measured by scintigraphy, as compared to placebo.
- 4. $T_{1/2}$ of gastric emptying of solid
- 5. Assess the effects on stool frequency and consistency based on the Bowel Pattern Diary and effects on symptom parameters coupled to constipation as well as the overall treatment effect, as compared to placebo based on a six question survey given at the end of the pre-treatment period and the post-treatment period.
- 6. Evaluate the pharmacokinetic (PK) characteristics and pharmacodynamic effects for each dose A3309.
- 7. Symptoms of constipation

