24.9 Assessment of sample size

Table 1 below summarizes data for the primary response measures and uses the (relative) variation, (CV%) to estimate the effect size detectable with 80% power based on a two sample t-test at a two-sided alpha level of 0.05. The effect size is the difference in group means as a percentage of the overall mean for each response and assumes 12 subjects per group. The ANCOVA should provide 80% power to detect similar (pairwise) differences using a pooled estimate of variation across all three groups and potentially even smaller effect sizes by adjusting for important covariates. The data from the scintigraphic transit studies are based on the same methods proposed for this study. There is no planned adjustment for dropouts. In these types of studies, we expect less than five percent dropouts. Missing data will be handled by standard imputation methods (e.g. use of mean data for all participants for that specific missing data), with appropriate adjustment of the degrees of freedom for each data imputed.

Table 6 Primary Response Measurement Summary

Assuming n=12/ group		Effect Size [‡] (%)		
		Detectable(N=12 per group) with:		
Response Type	CV%	80% Power (α =0.05)		
GE solids t _{1/2} min [†]	25	27		
GC @ 24 hrs †	35	37		
‡ Effect Size is the difference between means	as a percentag	e of listed mean		

^{†*} Based on data from previous studies (31,32,33) using similar methods to those proposed here. Transit data[†] from C-IBS studies (e.g. Renzapride, prucalopride, Tegaserod).

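### The synopsis claims 80% power for a 27% difference in the primary endpoint, but that figure belongs to gastric emptying; for GC24 the power is about 44% to 60%

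*Combined protocol and SAP*

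**What the plan says.** The Statistical Power paragraph of the synopsis says that "12 patients per group provides 80% power to detect differences of approximately 27% to 37% in colonic transit, the primary endpoints", and adds: "This magnitude of change is considered clinically significant".

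Section 24.9 introduces its table with "Table 1 below summarizes data for the primary response measures" (the table is numbered 6). Its two rows are:

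| Response | CV | Detectable difference, 12 per group, 80% power |
|---|---|---|
| Gastric emptying of solids, t1/2 | 25% | 27% |
| GC24 | 35% | 37% |

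The calculation is described as one "to estimate the effect size detectable with 80% power based on a two sample t-test at a two-sided alpha level of 0.05". The text says "The effect size is the difference in group means as a percentage of the overall mean for each response", while the table footnote refers to a listed mean.

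Section 9.2 gives one primary endpoint: "Colonic geometric center at 24 h as measured by scintigraphy, as compared to placebo". Section 9.3 has T1/2 "of gastric emptying of solid" as secondary endpoint 4. Section 24.4 and the synopsis endpoint list agree with both.

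**The concern.** The synopsis range is the two rows of Table 6 joined together. Its lower end comes from a measure that is neither colonic nor primary. Section 24.5 also names ascending colon emptying t1/2 as a primary summary, but Table 6 has no row for it, so 27% does not come from there. Amendment 1 does not revise the sentence.

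Anyone relying on the synopsis would believe that a 27% change in GC24 is both clinically meaningful and detectable with 80% power. If GC24 then turned out non-significant, the result could be read as ruling out a change of that size.

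**Working it through.** **Inputs.** 12 per group in three groups (synopsis); two-sided alpha 0.05, two-sample t-test, CV 25% and 35%, printed differences 27% and 37% (section 24.9); Dunnett's test for each dose against placebo (section 24.1).

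**Method.** Power comes from the noncentral t with df = 22 and noncentrality d × √(12/2). The standardized difference with 80% power is d = 1.1968.

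Let x = d × CV be the difference relative to the mean that defines the CV. If the effect is quoted on an overall mean that moves with treatment, effect = x / (1 + a·x), and so x = effect / (1 − a·effect). Four readings were computed:

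- A: a = 0, one mean for both effect and CV
- B: a = 1/3, CV on the placebo mean, effect on the three-group mean, one dose shifted
- C: a = 1/2, CV on the placebo mean, effect on a two-group mean
- D: a = 2/3, CV on the placebo mean, effect on the three-group mean, both doses shifted

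**Reproducing Table 6.**

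- A: 1.1968 × 25% = 29.9%; 1.1968 × 35% = 41.9%. Not the printed values.
- B: 0.2992 / (1 + 0.2992/3) = 27.2%; 0.4189 / (1 + 0.4189/3) = 36.8%. Both rows reproduced.
- C: 26.0% and 34.6%.
- D: 24.9% and 32.7%.

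A one-sided test on one mean also comes close (26.2% and 36.7%), but it contradicts the stated two-sided alpha. Table 6 is therefore ambiguous about its denominators and is not shown to be wrong.

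**Power for a 27% difference in GC24 (CV 35%).** Under B, for example, x = 0.27 / (1 − 0.09) = 0.2967 and d = 0.2967 / 0.35 = 0.848. The Dunnett column is power per dose-placebo comparison (two comparisons, df 33, critical value 2.310).

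| Reading | d | t-test power | Dunnett power |
|---|---|---|---|
| A | 0.771 | 43.9% | 34.9% |
| B | 0.848 | 51.0% | 41.8% |
| C | 0.892 | 55.1% | 45.9% |
| D | 0.941 | 59.6% | 50.5% |

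Using a pooled error with df 33 moves the t-test range only to 45%–61%.

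**What covariates would have to do.** For 80% t-test power at 27%, the residual CV must be x / 1.1968, that is 22.6%, 24.8%, 26.1% or 27.5% for A to D. The share of variance to be explained is 1 − (residual CV/35)², or 58%, 50%, 44% or 38%, ignoring degrees of freedom spent on covariates.

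**Power for the printed GC24 figure of 37%.** In the order A to D, t-test power is 70%, 81%, 86% and 91%; Dunnett power per comparison is 61%, 74%, 80% and 86%.

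**The case against.** The strongest reply is that this is a slip in a summary. Section 24.9 labels each row correctly and gives GC24 its own CV and difference, and nothing in the design or analysis depends on the synopsis sentence. That is so, and it keeps the point to a wording correction. It does not make the sentence true.

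A second reply is that section 24.9 expects "potentially even smaller effect sizes by adjusting for important covariates". The plan gives no covariate correlation. Of the covariates named in section 24.1, only age and BMI apply to GC24; the others are baseline diary summaries for the diary responses, and baseline GC24 is not listed. Nothing in the plan supports their explaining 38% to 58% of the variance.

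A third is that the power depends on the reading. It does: expressing the effect on the treated-arm mean gives 70%. The documents do not use that denominator, and 70% is still short of 80%. Likewise, if both doses work, the chance that at least one beats placebo is higher than the per-comparison Dunnett figure: 66% by simulation under reading D, against 50%. That matters for reading an overall null result, but it also misses 80%, and section 24.9 makes its claim for pairwise differences.

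Two limits stand. All figures hold the planning CV at 35%, which the plan takes from earlier studies. Also, the missing statement of denominators is a gap in detail, and sizing on a t-test is openly declared, so restating the figure for Dunnett's test is an improvement and not the correction of an error.

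**Conclusion.** The concern holds. The 27% is Table 6's gastric emptying figure, a secondary endpoint, and the synopsis wrongly presents it as a colonic, primary-endpoint figure with 80% power. For GC24, a 27% difference has 44% two-sided t-test power if one mean serves both effect and CV, and 51% to 60% on the overall-mean readings computed; under Dunnett's test it has 35% to 50% per comparison. Reaching 80% by t-test would take about 28 per group under reading A, or 23 under the reading that reproduces Table 6, against the planned 12. The misattribution is plain from the documents; the power figures assume CV 35%, no covariate gain and one of the stated denominators. Table 6's 37% for GC24 stands on the reading that reproduces both rows.

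**What to change.** In the synopsis, give only the GC24 figure for colonic transit, refer to the primary endpoint in the singular in that sentence, and identify 27% as gastric emptying t1/2, a secondary endpoint. In section 24.9, describe GC24 as the single primary response.

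In section 24.9 and Table 6, state which mean is the denominator of the CV and which of the effect. It would then help to restate the GC24 difference detectable with 80% power under Dunnett's test on that basis, before any covariate gain:

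| Reading | t-test | Dunnett |
|---|---|---|
| A: one mean for both | 42% | 45% |
| B: three-group mean, one dose shifted | 37% | 39% |
| C: two-group mean | 35% | 37% |
| D: three-group mean, both doses shifted | 33% | 35% |

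The cost is wording in the synopsis, section 24.9 and Table 6. Sample size, endpoint, alpha and analysis stay as they are. The synopsis loses the 27% figure for the primary endpoint, and on readings A and B the Dunnett figure is less favourable than the printed 37%. The plural wording about primary endpoints in the multiplicity sentence of section 24.1, repeated in the synopsis, is a separate matter and is not addressed here.

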4 ABBREVIATIONS AND TERMS

Abbreviation/Term	Definition	
A3309	Investigative drug substance code	
A3309- ¹⁴ C	Carbon-labeled drug substance	
AE	Adverse event	
ALT	Alanine aminotransferase	
ANCOVA	Analysis of covariance	
ANOVA	Analysis of variance	
AP	Alkaline phosphatase	
aPPT	Activated partial thromboplastin time	
AST	Aspartate aminotransferase	
BM	Bowel movement: A single defecation event with a beginning and end (as interpreted by the patient), which may include single or multiple stools.	
BMI	Body mass index	
bp	Blood pressure	
C4	7α-hydroxy-4-cholesten-3-one	
CIC	Chronic idiopathic constipation	
C_{max}	Maximum plasma concentration observed post-dose	
CRO	Contract research organization	
CSBM	Complete spontaneous bowel movement: A spontaneous bowel movement that is accompanied by the patient reporting a feeling of complete evacuation.	
CV	Cardiovascular	
CYP_{450}	Cytochrome P ₄₅₀	
ECG	Electrocardiogram	
GCP	Good Clinical Practice	
GI	Gastrointestinal	
HbA _{1c}	Glycosylated hemoglobin	
IB	Investigator's Brochure	
IBAT	Ileal bile acid transporter	
IBS	Irritable bowel syndrome	
IC ₅₀	Concentration for 50% inhibition of the effect	
ICF	Informed consent form	

Abbreviation/Term	Definition
IRB	Institutional Review Board
ITT	Intent to treat analysis
i.v.	Intravenous
LDL-C	Low density lipoprotein cholesterol
NOAEL	No observed adverse effect level
NOEL	No observed effect level
PD	Pharmacodynamic
PK	Pharmacokinetic
SAE	Serious adverse event
SBM	Spontaneous bowel movement: A bowel movement that occurs in the absence of a laxative/enema use or manual disimpaction. For the purpose of this protocol, bowel movements that occur within 24 hours of laxative/enema use will not be considered spontaneous bowel movements.
SAP	Statistical Analysis Plan
$t_{1/2}$	Half-life
t_{max}	Time to maximum observed plasma concentration

5 ETHICS

5.1 Ethical review

Necessary approvals of the study protocol and the informed consent form (ICF) must be obtained before enrollment of any patient into the study. It is the responsibility of the Principal Investigator (PI) to keep the Institutional Review Board (IRB) informed of any Serious Adverse Events (SAEs) and any substantial amendments to the protocol during the study period.

The written approval from the IRB, including study identification and the date of review will be filed at the study site together with a list of the IRB members, their titles or occupation, and their institutional affiliations. All correspondence with the IRB should be filed both at the Sponsor and at the study site.

5.2 Ethical conduct of the study

The study will be performed in accordance with the recommendations guiding physicians in biomedical research involving human subjects that were adopted in 1964 by the 18th World Medical Assembly, in Helsinki, Finland, with later revisions.

5.3 Patient information and consent

Informed consent will be obtained by the Investigator or study coordinator following both a review of the written ICF and a conversation outlining the risks, benefits, and goals of the investigation. The patient will be informed about the right to withdraw from the study at any time and should be allowed sufficient time for consideration of the proposal. Documentation will be recorded with signatures of the study participant and the individual obtaining consent (on the standard informed consent document) before any study-specific procedures are performed, including screening procedures.

The official Mayo IRB reviewed and approved version of the ICF must be used to obtain and document patient consent. The ICF must not be changed without permission from the sponsor Albireo AB and subsequent review and approval by Mayo IRB.

5.4 Patient data protection

The Investigator must file a patient identification list which includes sufficient information to link records, i.e. the Case Report Form (CRF) and the electronic medical record (EMR). This list will be preserved for possible future inspections/audits but should not be made available to the Sponsor except for monitoring or auditing purposes.

All data retrieved during the study will be used specifically for research purposes. Results will be maintained in Excel spreadsheets and SAS datasets stored electronically and will be password protected.

Mayo Clinic IRB guidelines for anonymizing data will be strictly adhered to. Only de-identified data will be permitted to be sent outside of Mayo Clinic. The ICF specifies that authorized representatives from the Sponsor, the IRB, FDA and other regulatory authorities will be granted access to the patient's medical record in a limited capacity for the purpose of verification of clinical study procedures.

